5.2 Trial Procedures

The Time & Events Table (Table 3) summarises the trial assessments and procedures to be performed at each visit. Individual trial procedures are described in detail below. It may be necessary to perform these procedures at unscheduled time points if deemed clinically or logistically necessary by the PI or delegate.

Furthermore, additional evaluations/testing may be deemed necessary by the Sponsor, PI or delegate and/or MSD for reasons related to subject safety. In some cases, such evaluations/testings may be potentially sensitive in nature (e.g., HIV, Hepatitis C, etc.), and thus local regulations may require that additional informed consent be obtained from the participant. In these cases, such evaluations/testings will be performed in accordance with those regulations.

Table 3: Time & Events

	Screening	TACE	Treatment Cycles ¹										End of Treatment	Post-Treatment		
Treatment Cycle Nos Week Nos	Screening		Day 1	1 ¹ , 10 Wk 0, 27	2 & 11 Wk 3, 30	3, 12 Wk 6, 33	4, 13 Wk 9, 36	5, 14 Wk 12, 39	To be repeated beyond 9 cycles and up to 17				Discontinuation	Safety Follow-up (SFU)	Follow Up Visits ¹⁰	Tel
Scheduling Window (Days): -28 to -1	Pre- TACE	N/A	Post TACE 30 + 3 (Part 1) Or Post TACE 45 + 3 (Part 2)	± 3	± 3	± 3	± 3	± 3	6, 15 Wk 15, 42	7, 16 Wk 18, 45	8, 17 Wk 21, 48	9 Wk 24				
Informed Consent	X												30 ± 7 post EOT	Q8W ± 7 post SFU		
Demographics and Medical History	X															
Tumour Imaging (mRECIST) ² (Chest CT and dual phase CT or contrast enhanced MRI scan of the abdomen)	X								X				X	X		
Assessment of Child-Pugh Score	X			X	X	X	X	X	X	X	X	X	X	X	X	
Full Physical Examination	X															
Directed Physical Examination				X	X	X	X	X	X	X	X	X	X	X	X	
Vital Signs, Weight & Height ¹²	X ¹²			X	X	X	X	X	X	X	X	X	X	X	X	
ECOG Performance Status	X			X	X	X	X	X	X	X	X	X	X	X	X	
12 – Lead ECG	X															
QoL Assessment: EORTC QLQ-C30 and QLQ-HCC18	X			X					X				X	X		
Pregnancy Test – Urine or Serum beta-HCG	X			X*												
Hepatitis Serology ³	X															
Viral Load (HBV DNA, HCV RNA) ⁴	X			X ¹					X				X	X		
PT/INR and aPTT	X			X ¹	X	X	X	X	X	X	X	X	X	X	X	
Alpha fetoprotein	X			X	X	X	X	X	X	X	X	X	X	X	X	
Haematology ⁵	X			X ¹	X	X	X	X	X	X	X	X	X	X	X	

Treatment Cycle Nos Week Nos	Screening	TACE	Treatment Cycles ¹										End of Treatment	Post-Treatment	

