6.6 Dose Modifications for Toxicity

Adverse events (both non-serious and serious) associated with Pembrolizumab exposure may represent an immunologic etiology. These AEs may occur shortly after the first dose or several months after the last dose. Pembrolizumab must be withheld for drug-related toxicities and severe or life-threatening AEs as per Table 8 below. See Section 6.8 for supportive care guidelines, including use of corticosteroids.

Treatment discontinuation for AST, ALT deterioration in participants who present with Grade 2 AST or ALT will be triggered only if AST or ALT increases by greater than or equal to 50% relative to the measurement taken at initiation of systemic treatment (Cycle 1 Day 1) and lasts for at least 1 week.

Toxicity	Hold Treatment For Grade	Timing for Restarting Treatment	Treatment Discontinuation
Diarrhoea/ Colitis	2-3	Toxicity resolves to Grade 0-1	Toxicity does not resolve within 12 weeks of last dose or inability to reduce corticosteroid to 10 mg or less of prednisone or equivalent per day within 12 weeks
	4	Permanently discontinue	Permanently discontinue
AST, ALT, or Increased Bilirubin	2	Toxicity resolves to Grade 0-1	Toxicity does not resolve within 12 weeks of last dose
	3-4	Permanently discontinue (see exception below) ^a	Permanently discontinue
Type 1 diabetes mellitus (if new onset) or Hyperglycaemia	T1DM or 3-4	Hold Pembrolizumab for new onset Type 1 diabetes mellitus or Grade 3-4 hyperglycemia associated with evidence of beta cell failure	Resume Pembrolizumab when participants are clinically and metabolically stable
Hypophysitis	2-4	Toxicity resolves to Grade 0-1. Therapy with Pembrolizumab can be continued while endocrine replacement therapy is instituted	Toxicity does not resolve within 12 weeks of last dose or inability to reduce corticosteroid to 10 mg or less of prednisone or equivalent per day within 12 weeks
Hyperthyroidism	3	Toxicity resolves to Grade 0-1	Toxicity does not resolve within 12 weeks of last dose or inability to reduce corticosteroid to 10 mg or less of prednisone or equivalent per day within 12 weeks
	4	Permanently discontinue	Permanently discontinue
Hypothyroidism		Therapy with Pembrolizumab can be continued while thyroid replacement therapy is instituted	Therapy with Pembrolizumab can be continued while thyroid replacement therapy is instituted

Toxicity	Hold Treatment For Grade	Timing for Restarting Treatment	Treatment Discontinuation

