Infusion Reaction	2 ^b	Toxicity resolves to Grade 0-1	Permanently discontinue if toxicity develops despite adequate premedication
	3-4	Permanently discontinue	Permanently discontinue
Pneumonitis	2	Toxicity resolves to Grade 0-1	Toxicity does not resolve within 12 weeks of last dose or inability to reduce corticosteroid to 10 mg or less of prednisone or equivalent per day within 12 weeks
	3-4	Permanently discontinue	Permanently discontinue
Renal Failure or Nephritis	2	Toxicity resolves to Grade 0-1	Toxicity does not resolve within 12 weeks of last dose or inability to reduce corticosteroid to 10 mg or less of prednisone or equivalent per day within 12 weeks
	3-4	Permanently discontinue	Permanently discontinue
All Other Drug-Related Toxicity ^c	3 or Severe	Toxicity resolves to Grade 0-1	Toxicity does not resolve within 12 weeks of last dose or inability to reduce corticosteroid to 10 mg or less of prednisone or equivalent per day within 12 weeks
	4	Permanently discontinue	Permanently discontinue

Note: Permanently discontinue for any severe or Grade 3 drug-related AE that recurs or any life-threatening event.

^a For participants who begin treatment with Grade 2 AST or ALT at Cycle 1 Day 1 of treatment, if AST or ALT increases by greater than or equal to 50% relative to baseline and lasts for at least 1 week then participants should be discontinued.

^b If symptoms resolve within one hour of stopping IMP infusion, the infusion may be restarted at 50% of the original infusion rate (e.g., from 100 mL/hr to 50 mL/hr). Otherwise dosing will be held until symptoms resolve and the participant should be pre-medicated for the next scheduled dose.

^c Participants with intolerable or persistent Grade 2 drug-related AE may hold study medication at PI/delegate discretion. Permanently discontinue IMP for persistent Grade 2 adverse reactions for which treatment with IMP has been held, that do not recover to Grade 0-1 within 12 weeks of the last dose.

Table 8: Dose Modification Guidelines for Drug-Related Adverse Events

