- When symptoms improve to Grade 1 or less, steroid taper should be started and continued over no less than 4 weeks.

6.8.1.3 Type 1 diabetes mellitus (if new onset, including diabetic ketoacidosis [DKA]) or \geq Grade 3 Hyperglycaemia, if associated with ketosis (ketonuria) or metabolic acidosis (DKA)

- For **T1DM or Grade 3-4 Hyperglycemia**
 - Insulin replacement therapy is recommended for Type 1 diabetes mellitus and for Grade 3-4 hyperglycaemia associated with metabolic acidosis or ketonuria.
 - Evaluate participants with serum glucose and a metabolic panel, urine ketones, glycosylated hemoglobin, and C-peptide.

6.8.1.4 Hypophysitis:

- For **Grade 2 events**, treat with corticosteroids. When symptoms improve to Grade 1 or less, steroid taper should be started and continued over no less than 4 weeks. Replacement of appropriate hormones may be required as the steroid dose is tapered.
- For **Grade 3-4 events**, treat with an initial dose of IV corticosteroids followed by oral corticosteroids. When symptoms improve to Grade 1 or less, steroid taper should be started and continued over no

less than 4 weeks. Replacement of appropriate hormones may be required as the steroid dose is tapered.

6.8.1.5 Hyperthyroidism or Hypothyroidism:

Thyroid disorders can occur at any time during treatment. Monitor participants for changes in thyroid function (at the start of treatment, periodically during treatment, and as indicated based on clinical evaluation) and for clinical signs and symptoms of thyroid disorders.

- **Grade 2** hyperthyroidism events (and **Grade 2-4** hypothyroidism):
 - In hyperthyroidism, non-selective beta-blockers (e.g. propranolol) are suggested as initial therapy.
 - In hypothyroidism, thyroid hormone replacement therapy, with levothyroxine or liothyroinine, is indicated per standard of care.
- **Grade 3-4** hyperthyroidism
 - Treat with an initial dose of IV corticosteroid followed by oral corticosteroids. When symptoms improve to Grade 1 or less, steroid taper should be started and continued over no less than 4 weeks. Replacement of appropriate hormones may be required as the steroid dose is tapered.

6.8.1.6 Hepatic:

- Comprehensive guidance on the diagnosis and management of hepatic events of interest are reported in Section 6.8.3.
- For **Grade 2** events, monitor liver function tests more frequently until returned to baseline values (consider weekly).
 - Treat with IV or oral corticosteroids

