6.8.2 Supportive Care Guidelines for Immune-related Adverse Event (irAE) and Immune-related Events of Clinical Interest (irECI).

Immune-related Adverse events (IrAEs) may be defined as an AE of unknown etiology, associated with IMP exposure and is consistent with an immune phenomenon. IrAEs may be predicted based on the nature of the Pembrolizumab compound, its mechanism of action, and reported experience with immunotherapies that have a similar mechanism of action. Special attention should be paid to AEs that may be suggestive of potential irAEs. An irAE can occur shortly after the first dose or several months after the last dose of IMP.

If an irAE is suspected, efforts should be made to rule out neoplastic, infectious, metabolic, toxin or other etiologic causes prior to labelling an AE as an irAE. Participants who develop a Grade 2 or higher irAE should be discussed immediately with the CI/designee.

Recommendations to managing irAEs not detailed elsewhere in the protocol are detailed in Table 10.

irAE	Withhold/Discontinue Pembrolizumab?	Supportive Care
Grade 1	No action	Provide symptomatic treatment
Grade 2	May withhold Pembrolizumab	Consider systemic corticosteroids in addition to appropriate symptomatic treatment. Steroid taper should be considered once symptoms improve to Grade 1 or less and tapered over at least 4 weeks.
Grade 3 and Grade 4	Withhold Pembrolizumab Discontinue if unable to reduce corticosteroid dose to < 10 mg per day prednisone equivalent within 12 weeks of toxicity	Systemic corticosteroids are indicated in addition to appropriate symptomatic treatment. May utilize 1 to 2 mg/kg prednisone or equivalent per day. Steroid taper should be considered once symptoms improve to Grade 1 or less and tapered over at least 4 weeks.

Table 10: General Approach for Handling irAEs

Details for managing specific irAEs are summarised below:

Immune-mediated pneumonitis

Monitor participants for signs and symptoms of pneumonitis. If pneumonitis is suspected, evaluate with radiographic imaging. Exclude other causes of pneumonitis, and manage treatment in accordance with the

guidelines above. Administer corticosteroids, withhold Pembrolizumab for moderate (Grade 2) pneumonitis, and permanently discontinue Pembrolizumab for severe (Grade 3) or life-threatening (Grade 4) pneumonitis.

Immune-mediated colitis

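### For participants who start with Grade 2 AST/ALT, Table 8's Grade 2 row sets a restart level and a 12-week stop that do not fit the baseline-referenced rule in section 6.6

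*Combined protocol and SAP*

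**What the plan says.** - **Section 6.6, text.** Holding drug for drug-related toxicity according to Table 8 is mandatory. For one subgroup the text adds: "Treatment discontinuation for AST, ALT deterioration in participants who present with Grade 2 AST or ALT will be triggered only if" the value is at least 50% above Cycle 1 Day 1 for at least 1 week.
- **Table 8, AST/ALT/bilirubin, Grade 2.** The restart cell reads "Toxicity resolves to Grade 0-1" and the discontinuation cell "Toxicity does not resolve within 12 weeks of last dose". Neither carries a footnote.
- **Table 8, same toxicity, Grade 3-4.** The cell reads "Permanently discontinue (see exception below" and carries footnote a. That footnote opens "For participants who begin treatment with Grade 2 AST or ALT at Cycle 1 Day 1 of treatment" and repeats the 50%/1-week rule. It is silent on holding and restarting.
- **Who is covered.** Section 4.1.1 (Table 2) admits AST and ALT up to 5 x ULN. Section 7.1 counts a clinically significant worsening of a pre-existing condition as an adverse event.
- **Recovery elsewhere.** For Grade 2 hepatic events, 6.8.1.6 says "monitor liver function tests more frequently until returned to baseline values (consider weekly". Section 6.8.3 refers recovery to baseline for immune-related hepatitis, to baseline grade within 12 weeks for viral flares, and to baseline grade within 3 weeks for other hepatic events. Section 7.1.3 follows laboratory abnormalities to baseline or to a level that the investigator accepts.
- **Referral.** Section 6.8.2 says "Participants who develop a Grade 2 or higher irAE should be discussed immediately with the CI/designee". Section 7.4 item 2 makes drug-induced liver injury with AST/ALT of at least 3 x ULN an event of clinical interest, and 7.5 sends it to the CI within 24 hours.
- **Schedule.** Table 3 is "To be repeated beyond 9 cycles and up to 17", with doses at weeks 0 to 48.

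**The concern.** Section 6.6 recognises that some participants start with raised transaminases and should be judged against their own start. Table 8 carries that idea into the Grade 3-4 row only. In the Grade 2 row, a participant who had a small drug-related rise and has fully returned to the Cycle 1 Day 1 value still does not meet the restart condition. If the value stays there for 12 weeks, the row discontinues treatment although the 6.6 condition was never met.

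What is at stake is doses for individual participants, consistent handling across one to four sites, and the descriptive summary in section 8.3 of how adverse events affected study drug.

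**Working it through.** The plan gives no figure to reproduce, so the check compares the rules and then applies simple arithmetic.

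**1. Which rises are caught.** Table 8 applies to drug-related toxicity, so an unchanged Grade 2 baseline does not trigger it. A clinically significant, drug-related rise that stays within Grade 2 does. If it is under 50%, 6.6 gives no ground to discontinue, but the Grade 2 row holds treatment. Rises that cross into Grade 3 fall in the other row and are outside this point.

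**2. Assumed cut-offs.** The documents do not print the CTCAE limits. Assume Grade 2 AST/ALT runs from above L = 3 to U = 5 x ULN, with L varied from 2.5 to 3 and U from 4.5 to 6. The textual conflict itself needs only that Grade 1 lies below Grade 2.

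**3. Fall below the starting value needed to restart**, 1 - L/start:

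| Start (x ULN) | L | Fall needed |
|---|---|---|
| 3.5 | 3 | 1 - 3/3.5 = 14% |
| 4.0 | 3 | 1 - 3/4.0 = 25% |
| 4.5 | 3 | 1 - 3/4.5 = 33% |
| 3.5 | 2.5 | 1 - 2.5/3.5 = 29% |

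**4. Where a rise within Grade 2 can never meet the 50% rule.** This holds when 1.5 x start > U, that is, for starts above U/1.5. The share of the band's width is (U - U/1.5)/(U - L):

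| L | U | U/1.5 | Share |
|---|---|---|---|
| 3 | 5 | 3.33 | 1.67/2 = 83% |
| 2.5 | 5 | 3.33 | 1.67/2.5 = 67% |
| 3 | 4.5 | 3.0 | 1.5/1.5 = 100% |
| 3 | 6 | 4.0 | 2/3 = 67% |
| 2.5 | 6 | 4.0 | 2/3.5 = 57% |

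The central figure is 83%, with a range of 57% to 100%.

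**5. Example.** ALT goes from 3.5 to 4.5 x ULN and back to 3.5. The rise is 4.5/3.5 - 1 = 29%. The 6.6 trigger would be 1.5 x 3.5 = 5.25 x ULN, which is not reached. The 6.8.3 trigger for someone starting at or above 2 x ULN is more than 3 x 3.5 = 10.5 x ULN, also not reached. The alternative 6.8.3 trigger, above 500 U/L, needs a laboratory ULN above 500/5 = 100 U/L while the value is still Grade 2. So the baseline-referenced restart rules in 6.8.3 do not apply to this case.

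**6. Doses.** Weeks 0, 3, ..., 48 give 17 doses.
- Hold after Cycle 1 (week 0): the doses at weeks 3, 6 and 9 are missed before the 12-week limit. If treatment then stops, 16 of 17 are lost.
- Hold after Cycle 9 (week 24): weeks 27 to 48, so 8 of 17 are lost.
- Release at the Cycle 1 Day 1 value: a rise that has cleared by the visit after the missed dose costs 1.

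**The case against.** The best counter-argument uses the drug-related filter on exit as well as on entry. Once AST/ALT is back at the Cycle 1 Day 1 value, what remains is the pre-existing abnormality, so the toxicity has resolved. That is a sensible clinical reading, but the restart cell names Grade 0-1, and a site following the table would not get there.

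The affected group may also be very small. A rise within Grade 2 must be judged both clinically significant and drug-related, and 6.8.3 does not suspect immune-related hepatitis in these participants until far larger rises. This stands: the number cannot be estimated.

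A reader might infer that a recovered participant can be neither restarted nor discontinued. The documents do not support that. Section 6.8.3 allows interruption and possible restart after discussion with the sponsor and CI. Section 7.4 item 2 brings drug-induced cases at or above 3 x ULN into the event-of-clinical-interest process. Section 6.11.1 lets the investigator stop treatment. What these routes lack is a restart value.

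A cautious hold is also defensible in a safety-oriented trial in participants with limited liver reserve. That lowers the importance but does not reconcile the two rules.

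**Conclusion.** The inconsistency is in the text. For a drug-related rise under 50% that stays within Grade 2, Table 8 read literally requires a value better than the participant's own start before restart, and it discontinues at 12 weeks where 6.6 says not to. The specific sentence in 6.6 probably prevails over the 12-week cell, but it says nothing about restart.

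Importance is minor. The row errs towards caution, and the Part 1 stopping rule counts DLTs and is unaffected. Only individual dosing and a descriptive summary change.

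Two figures invite over-reading. The 83% is a share of the assumed Grade 2 band, not of participants, since no baseline AST/ALT distribution is given. The loss of 16 of 17 doses is the worst case, a hold straight after Cycle 1 that never lifts, and not an expected loss. The percentages rest on the assumed cut-offs.

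**What to change.** Mark the Grade 2 AST/ALT row with footnote a and extend the footnote for participants with Grade 2 AST or ALT at Cycle 1 Day 1:

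1. A hold for a drug-related rise ends when the value is at Grade 0-1, or at or below the Cycle 1 Day 1 value.
2. Discontinuation follows the 50%/1-week rule in 6.6. The 12-week cell does not by itself force it. A hold still open at 12 weeks is decided with the sponsor and CI, as in 6.8.3.
3. Events that meet the 6.8.3 triggers are handled there (cross-reference).

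Leave the 6.6 sentence unchanged; adding a 12-week criterion to it would reverse its explicit restriction. Baseline grade alone is not a usable restart target in this row, because a rise within Grade 2 already meets it when the hold begins. The price is a recovery standard that differs from the viral-flare rule in 6.8.3, where baseline grade is enough.

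The cost is one footnote mark, one extended footnote and one cross-reference at the next amendment, with no added visits, data or participants. The downside is a slightly less strict restart condition for these participants.

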Thyroid disorders have been reported in participants receiving Pembrolizumab and can occur at any time during treatment; therefore, monitor participants for changes in thyroid function (at the start of treatment, periodically during treatment and as indicated based on clinical evaluation) and clinical signs and symptoms of thyroid disorders. Administer corticosteroids, withhold Pembrolizumab for severe (Grade 3) hyperthyroidism, and permanently discontinue Pembrolizumab for life-threatening (Grade 4) hyperthyroidism. Treat symptoms of hyperthyroidism as appropriate. Isolated hypothyroidism may be managed with replacement therapy without treatment interruption and without corticosteroids. For participants with severe (Grade 3) or life-threatening (Grade 4) endocrinopathy that resolved and is controlled with hormone replacement, continuation of Pembrolizumab may be considered.

Other immune-mediated adverse events

Across clinical studies with Pembrolizumab in approximately 5000 participants, the following additional clinically significant, immune-mediated adverse reactions were reported in less than 1% of participants: uveitis and severe skin reactions.

In addition a set of irAEs have also been classified as immune-related events of clinical interest (irECI) a full list of these can be found in Table 12 in section 7.4. Participants with symptomatic irECIs should immediately stop receiving Pembrolizumab and be evaluated to rule out non treatment related causes of the event. All irECIs irrespective of relationship to the IMP should be reported within 24 hours of the PI/delegate being aware to the Sponsor/CI who will in turn notify MSD. If the irECI is determined to be associated please refer to section 6.8.3. If the event is not considered to be related with the IMP the PI/delegate should exercise individual clinical judgment on the event management based on the participant. Any additional questions of the collection or information on management of irECIs should be directed to the CI/delegate.

6.8.3 Guidance for Diagnosis and Management of Hepatic Events of Clinical Interest.

In addition to overdose, hepatic ECIs will include any of the following events. All of these events will require holding Pembrolizumab treatment, notification of the Sponsor, CI/delegate within 24 hours, and a hepatology consultation. Refer to Section 7 for reporting guidelines.

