7.2.1.1 Determining AE Severity and Grade

AE severity and grade will be evaluated according to the NCI CTCAE version 4.0. Any AE which changes CTCAE grade over the course of a given episode should be closed at the date and time the severity changed and a new AE recorded from the date and time of the new NCI CTCAE grade.

Grade 1	Mild; asymptomatic or mild symptoms; clinical or diagnostic observations only; intervention not indicated.
Grade 2	Moderate; minimal, local or non-invasive intervention indicated; limiting age-appropriate instrumental ADL.
Grade 3	Severe or medically significant but not immediately life-threatening; hospitalisation or prolongation of hospitalisation indicated; disabling; limiting self-care ADL.
Grade 4	Life threatening consequences; urgent intervention indicated.
Grade 5	Death related to AE

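### Table 8 allows pembrolizumab to resume after Grade 4 hypophysitis or Grade 4 hyperglycaemia with beta cell failure, while the table's own note stops treatment permanently for any life-threatening event

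*Combined protocol and SAP*

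**What the plan says.** Table 8 in section 6.6 sets hold, restart and discontinuation rules by toxicity and grade.

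- **Hypophysitis.** One row covers Grades 2 to 4. Its restart cell asks for resolution to Grade 0-1 and then reads "Therapy with Pembrolizumab can be continued while endocrine replacement therapy is instituted". Permanent discontinuation follows only from non-resolution, or failure to taper the steroid, within 12 weeks.
- **Type 1 diabetes or hyperglycaemia.** Treatment is held for new-onset type 1 diabetes or "Grade 3-4 hyperglycemia associated with evidence of beta cell failure". The row then says "Resume Pembrolizumab when participants are clinically and metabolically stable".
- **Hyperthyroidism.** Grade 3 is a hold; Grade 4 is a permanent stop.
- **Note under the table.** "Permanently discontinue for any severe or Grade 3 drug-related AE that recurs or any life-threatening event".

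Section 7.2.1.1 defines Grade 4 as "Life threatening consequences; urgent intervention indicated".

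Section 6.8.2, under immune-mediated endocrinopathies, covers the same events again. For Grade 3 and Grade 4 hypophysitis it offers either withholding or discontinuing. For severe hyperglycaemia it withholds until metabolic control returns. For hyperthyroidism it says "permanently discontinue Pembrolizumab for life-threatening (Grade 4) hyperthyroidism". Later in that thyroid paragraph a general sentence, covering Grade 3 as well, says that for "life-threatening (Grade 4) endocrinopathy that resolved and is controlled with hormone replacement, continuation of Pembrolizumab may be considered".

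**The concern.** A rule for stopping treatment after a life-threatening event should give one answer. Here an investigator who follows the row may restart, and one who follows the note must stop for good. Patient safety is the first thing at stake.

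The second is the primary endpoint, safety and tolerability. Section 8.3 summarises adverse events by, among other things, their impact on the study drug. With up to four sites, the same Grade 4 event could be recorded as a temporary hold at one and a permanent discontinuation at another, with both sites able to cite the protocol.

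**Working it through.** The point depends on no sample-size or power figure, and the plan states no figure to reproduce. The check is a comparison of texts.

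**Step 1: does the note reach Grade 4?** The note speaks of life-threatening events, not grades. Section 7.2.1.1 defines Grade 4 in those terms, and 6.8.2 repeatedly pairs the word with Grade 4 in brackets. On the protocol's own usage, a Grade 4 event is a life-threatening event.

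**Step 2: set the instructions side by side.**

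| Grade 4 event | Table 8 row | Table 8 note | Section 6.8.2 |
|---|---|---|---|
| Hypophysitis | Restart permitted at Grade 0-1 | Permanent stop | Withhold or discontinue; general sentence allows continuation to be considered |
| Hyperglycaemia with beta cell failure | Resume once stable | Permanent stop | Withhold until controlled (worded for severe hyperglycaemia) |
| Hyperthyroidism | Permanent stop | Permanent stop | Permanent stop by name; general sentence allows continuation to be considered if resolved and on replacement |

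In the first two lines the row and the note of one table are incompatible. In the third, the row, the note and the named sentence of 6.8.2 agree. Only the general sentence departs from them, and only when its conditions are met. Section 6.8.1.5 says hormone replacement may be needed after Grade 3-4 hyperthyroidism, so those conditions can be met.

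**Step 3: does the table settle precedence?** It does not.

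- Where an exception was intended it was marked: the AST/ALT/bilirubin row points to a footnote. The hypophysitis and diabetes rows carry no such pointer.
- Every other row that lists Grade 4 already stops permanently at that grade: colitis, AST/ALT/bilirubin (subject to its marked exception), hyperthyroidism, infusion reaction, pneumonitis, renal, and all other drug-related toxicity. For drug-related Grade 4 events in graded rows, the life-threatening clause therefore adds something almost only in the hypophysitis and diabetes rows. If those rows are silent exceptions, the clause does little. (The hypothyroidism row lists no grade and is left out of this comparison.)

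**Step 4: size.** One participant classified differently changes the permanent-discontinuation proportion by 1/32 = 3.1 percentage points, on 32 evaluable participants. The documents give no rate for Grade 4 endocrine events. As a loose ceiling, section 1.2.2 reports Grade 3-5 drug-related events of all types in 6.8% to 12.0% of participants across pembrolizumab monotherapy studies. If that range applied here, it would mean 0.068 × 32 = 2.2 to 0.120 × 32 = 3.8 participants with any such event. The commonest types listed there are anaemia, ALT and AST rises, and colitis, none of them endocrine. Grade 4 endocrine events would be a fraction of this, possibly none.

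**The case against.** The strongest reply is that the specific row overrides the general note. The hypophysitis and diabetes rows visibly depart from the table's usual pattern of stopping at Grade 4, and 6.8.2 departs from it again for the same events. The drafters' intention may well be legible, with only an exception clause missing from the note. That is a fair account of how the text may have arisen. It does not remove the conflict: the note says any, no precedence is written, and the one exception the table recognises is marked.

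A second reply is that section 6.8.2 requires any immune-related event of Grade 2 or higher to be discussed at once with the chief investigator or designee. This stands as partial mitigation, since cases reach a central decision-maker. That person, however, has the same two texts.

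A third is that no decision rule uses the discontinuation count. The Part 1 decision rests on dose-limiting toxicities and the safety committee's review, and the analysis is descriptive. This also stands, and it limits the statistical consequence.

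Three stronger readings are tempting and are not supported:

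- *That every Grade 4 endocrine event receives incompatible instructions.* The hold text for hyperglycaemia is limited to cases with beta cell failure, and hyperthyroidism conflicts only under the conditions of the general sentence.
- *That 6.8.2 flatly contradicts itself on hyperthyroidism.* The later sentence is permissive, requires resolution and control on replacement, does not name hyperthyroidism, and directly follows a sentence about hypothyroidism. The fault is that it does not except hyperthyroidism.
- *That the hypophysitis restart cell orders both a hold and uninterrupted treatment.* Under its column heading it can be read as restart on resolution, with replacement therapy still running.

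**Conclusion.** The plan is wrong as written on the main point. For Grade 4 hypophysitis, and for Grade 4 hyperglycaemia with beta cell failure, a row of Table 8 and the note to Table 8 give opposite instructions, and nothing in the protocol ranks them. Section 6.8.2 adds a further wording for hypophysitis. The hyperthyroidism overlap is real but narrower and secondary.

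The conclusion rests on reading life-threatening as Grade 4, which the protocol does itself, and on the absence of any stated precedence. Such events should be few among 32 participants, so the expected effect on the tolerability summary is small. The case for correction is that the rule governs treatment after a life-threatening event. Nothing here implies which instruction is clinically right.

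**What to change.** Reconcile the passages, leaving the clinical choice to the sponsor:

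1. State in Table 8 whether the note governs the hypophysitis and diabetes/hyperglycaemia rows or those rows are exceptions to it. If they are exceptions, mark them as the AST/ALT/bilirubin row is marked.
2. Make the hypophysitis and hyperglycaemia sentences in 6.8.2 say the same as the reconciled table at Grade 4.
3. State whether the general endocrinopathy sentence in 6.8.2 applies to Grade 4 hyperthyroidism.

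The cost is a few lines of wording in Table 8 and the endocrinopathy text of 6.8.2, made through a protocol amendment. Data collection, sample size and analysis methods do not change. If any such event has already occurred, record which instruction was followed so that the summary by impact on study drug can be interpreted.
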